	gamma globulins, or anticonvulsive drugs within the				
	previous 6 months.				
Endpoints	Primary Endpoint: Cumulative number of RTIs over the 12				
	months.				
	monuis.				
	Secondary Endpoints:				
	• Duration in days of RTIs				
	• Antibiotic use (n. of cycles and days)				
	Missed school/work days				
	• Adenoid and tonsil survey (described in appendix 1 of the				
	original protocol)				
	• Size of adenoid tissue over the 12 months according to				
	radiographic and flexible nasopharyngoscopic evaluation (described				
	in appendix 3 of original protocol).				
	Surgery need				
	• AEs				
	Patients will be recruited from 01 September 2017 to 01 March				
Procedures	2018. The trial will begin in 01 September 2017 and will be				
	completed 01 March 2019.				
	Children with the ages of 2-6 years who have recurrent RTIs and				
	AH will be evaluated for the eligibility for the study. When eligible				
	for the study, children's all demographic characteristics will be				
	recorded (Table 1). Eligible children will be evaluated by ear-nose-				
	throat (ENT) specialist and flexible laryngoscopy and radiographic				
	evaluation of adenoid size will be performed in order to measure the				
	adenoid size. All children will be evaluated by an allergy specialist.				
	Complete blood count, serum IgG, IgA, IgE, IgM will be measured.				

Skin prick test will be performed with common allergens.

All children will be randomized into two study arms (active treatment and placebo). OM-85 3.5 mg capsule or placebo will be given according to the standard treatment schedule (10-10-10) for the three consecutive months. All patients will receive 2 cures of treatment at the beginning and 6 Months after inclusion in the study. Every patients will be followed-up for 12 months.

Patients (and care giver/parents) will be given a symptom score form (Table 2) in order to record all nasal symptoms, signs and duration of RTIs, antibiotic use, days of absenteeism from school and from work for family members, monthly.

All patients will be asked to come to the clinic when they have symptoms of RTI in order to diagnose the type of RTIs. Then they will be asked to complete the infection form during the acute RTIs (Table 3).

Every 3 months they will fill in the Tonsil and Adenoid Health Status Survey (Table 4).

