Every 3 months patients will be asked to come to the clinic and all their records will be collected and they will be evaluated by the ENT specialist for the adenoid tissue size. All these parameters will be recorded in specific forms by the investigator (Table 5).

Patients will be allowed to use nasal corticosteroids, antihistaminic drugs and flu vaccine during the study period and all these study medications will be recorded.

At the end of the study (12 months), immunoglobulin levels will be measured to compare them with basal level.

	1				
Sample Size	A total of 68 patients will be randomized in the study in a 1:1 ratio				
	to Active or Placebo groups.				
	Active group: 34 patients				
	Placebo group: 34 patients				
N ^o Sites					
	Number of study centers: 1				
	Study center: [name] Maternity and Children Research and				
	Training Hospital, Department of Pediatric Allergy and				
	Immunology, Ankara, TURKEY.				
	Study Coordinator and Principal Investigator:				
	[name] M.D. Associate Prof. of Pediatrics and Pediatric				
	Allergy, Training staff on Pediatric Allergy				
	Other Investigators:				
	[name] M.D. Professor of Pediatrics & Subspecialist on				
	Pediatric Allergy and Pediatric Pulmonology				
	Chief of Pediatric Allergy and Immunology Department				
	[name] M.D. Otolaryngologist				
	[name] M.D. Radiologist				
	Statistical method:				
Statistical Methods	All analyses will performed with a commercially available software				
	program (SPSS Statistical Software, version 11.5; SPSS, Inc,				
	Chicago,Ill).				
	The Shapiro-Wilks test will use to evaluate normality of the				
	distributions collected. When variables were normally distributed,				
	they were expressed as means (SDs); otherwise, they will express as				
	medians and interquartile ranges (25th-75th percentiles). The x^2 test				
	will use for categorical variables and expressed as observation				
	counts (in percentages). An ANOVA (or Mann-Whitney U				
	depending on the normality of data) statistics will be used to				
	compare means between both treatment groups for continuous				
	variables. Bonferroni multiple comparison test will use to compared				
	paired intervals (0-3, 0-6 months). All P values are 2-tailed; a P				
	pared intervals (0.5, 0.0 inontins). An 1 values are 2-tailed, a 1				

	value of loss than 05 are considered statistically significant					
	value of less than .05 are considered statistically significant.					

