Statistical method:

All analyses will be performed with a commercially available software program (SPSS Statistical Software, version 11.5; SPSS, Inc, Chicago, Ill). The Shapiro-Wilks test will be used to evaluate normality of the distributions collected. When variables were normally distributed, they were expressed as means (SDs); otherwise, they will be expressed as medians and interquartile ranges (25th-75th percentiles). The χ^2 test will be used for categorical variables and expressed as observation counts (in percentages). An ANOVA (or Mann-Whitney U depending on the normality of data) statistics will be used to compare means between both treatment groups for continuous variables. Bonferroni multiple comparison test will be used to compare paired intervals (0-3, 0-6 months). All P values are 2-tailed; a P value of less than .05 are considered statistically significant.

Sample Size:

In one study OM-85 group showed 3 less RTIs compared with placebo over 12 months period. A sample size of 54 randomized patients (27 per group) will provide at least 80% power to detect a mean difference of at least 2.0 RTIs between the two groups assuming a SD of 2.55 and assuming a drop-rate of 20% after 6 months, total of 68 patients (34 per group) will be recruited to the study.¹

Reference:

María Dolores Gutiérrez-Tarango and Arturo Berber. Safety and Efficacy of Two Courses of OM-85 BV in the Prevention of Respiratory Tract Infections in Children During 12 Months. CHEST 2001; 119:1742–1748

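### The one comparison named for month-12 immunoglobulins is with baseline; a baseline-adjusted comparison between arms should be stated instead

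*Protocol*

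**What the plan says.** At entry (Protocol, Procedures): "Complete blood count, serum IgG, IgA, IgE, IgM will be measured". The baseline form (Appendix 1, Table 1) has fields for all four immunoglobulins. At the 12-month visit, "immunoglobulin levels will be measured to compare them with basal level". That sentence names neither arm and gives no test.

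The design supplies a concurrent control: "All children will be randomized into two study arms (active treatment and placebo", and "Every patients will be followed-up for 12 months".

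The SAP, like the Statistical Methods section of the protocol, has a general rule: ANOVA, or Mann-Whitney U, "will be used to compare means between both treatment groups for continuous variables". It also provides for paired comparisons: "Bonferroni multiple comparison test will be used to compare paired intervals (0-3, 0-6 months"). Month 12 is not among those intervals. The significance rule is "All P values are 2-tailed; a P value of less than .05 are considered statistically significant".

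Immunoglobulins appear neither under Objectives nor under Endpoints, and the follow-up form (Appendix 1, Table 5) has no field for them.

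**The concern.** A before-after comparison answers the question of whether levels changed, not whether OM-85 changed them. Over 12 months in children aged 2-6, immunoglobulins may move with growth and with infections during the year, whatever the treatment. Within one arm these causes cannot be told apart from a drug effect. The placebo arm can separate them, and it is sampled at both times.

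What is at stake is an explanatory claim rather than the primary result. The research question and rationale are immunological, and the month-12 immunoglobulins are the only immune measurement planned after treatment. A rise from baseline in the OM-85 arm could easily be read as support for the mechanism. The general between-group rule offers a valid alternative, but it leaves open which quantity is compared and makes no use of the baseline value.

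**Working it through.** **1. The plan's own figure.** The documents give no figure for immunoglobulins. The stated sample size concerns the primary endpoint: difference 2.0, SD 2.55, two-sided alpha 0.05, power 80%. The t-test calculation gives 26.5, so 27 per arm, with power 80.7% at 27. Dropout of 20% gives 27 / 0.8 = 33.75, so 34 per arm and 68 in total. Both stated figures reproduce. I use 27 per arm for completers and 34 for no dropout.

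**2. Where the plan leaves the analysis open.**
- The sentence specific to immunoglobulins names a comparison with baseline and no arm.
- The general rule names a comparison between arms, but not whether of the month-12 level or the change, and with no covariate.
- The paired comparisons are for 0-3 and 0-6 months. Immunoglobulins are planned only at 0 and 12 months, so no paired method is given for them.

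**3. What a within-arm test would do with no drug effect.** Assumptions, none of them in the documents: baseline and month-12 values have equal SD, their correlation is r = 0.7, and both arms drift by d SD for reasons other than treatment.

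SD of change = sqrt(2(1 − r)) = sqrt(0.60) = 0.775, so the standardised change is d / 0.775. Chance that a two-sided paired t-test at 0.05 is significant in one arm:

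| Drift d (SD) | d / 0.775 | 27 per arm | 34 per arm |
|---|---|---|---|
| 0 | 0 | 5% | 5% |
| 0.2 | 0.258 | 25.3% | 31% |
| 0.3 | 0.387 | 49.1% | 59% |
| 0.4 | 0.516 | 73.3% | 83% |

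The result depends on r. At r = 0.5 the SD of change is 1, and the rates at 27 per arm for the three non-zero drifts are 17%, 32% and 52%.

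A between-arm test on change stays at about 5% throughout, because the common drift cancels. Simulation of 40,000 null trials per setting gave 4.9% to 5.1%.

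**4. The split pattern.** Testing each arm against its own baseline and contrasting the two results does not repair this. With p the rate at 27 per arm, the null probability of significance in the OM-85 arm but not in the placebo arm is p(1 − p):
- d = 0.2: 0.253 × 0.747 = 0.19
- d = 0.3: 0.491 × 0.509 = 0.25
- d = 0.4: 0.733 × 0.267 = 0.20

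**5. What baseline adjustment gains.** Relative variance of the between-arm difference at r = 0.7:
- month-12 level, unadjusted: 1
- change score: 2(1 − 0.7) = 0.60
- ANCOVA: 1 − 0.7² = 0.51

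ANCOVA therefore has 51% of the variance of the unadjusted month-12 comparison and 0.51 / 0.60 = 85% of that of the change score.

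**The case against.** The strongest reply is that the plan already contains the randomised comparison. The general rule makes no exception, immunoglobulins are continuous, and so they are to be compared between arms. The sentence in Procedures explains why a second sample is taken. Comparing with baseline may simply be the first step of a change score that is then compared between arms. No document prescribes a 0-12 month paired test, so the error rates above describe a test that might be used, not one that is planned.

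Much of this stands. A reader might infer that immunoglobulins are to be compared only with the child's own baseline. The protocol does not say so, and the general rule points the other way. A reader might also infer that season is a source of bias, since children enter between September and March. That does not follow: each child's second sample is due 12 months after the first, at about the same time of year. Season could enter only through mistimed visits or differences between years.

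It is also fair that a between-arm test without adjustment is valid in a randomised trial, so the adjustment is a gain in precision. The often-quoted halving of variance holds only against the unadjusted month-12 comparison; against a change score the gain is about 15%.

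What the reply does not remove is that the one sentence specific to this measurement names a comparison that cannot answer the treatment question, and that the general rule does not say what it is applied to.

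**Conclusion.** The point holds as a small clarification. The comparison named for month-12 immunoglobulins is with baseline and cannot distinguish drug effect from growth or intervening infections. The general rule reaches these variables but is unadjusted and silent on level versus change.

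The size is conditional. Error rates of about 25% to 73% apply only if a within-arm paired test is used, with 27 completers, a correlation of 0.7 and a common drift of 0.2 to 0.4 SD. With no drift the rate is 5%. Drift and correlation are assumptions. The variance figures of 51% and 85% rest on the same assumed correlation.

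Immunoglobulins are not a listed endpoint, and neither the primary analysis nor the sample size is affected. The change is worth making because it costs almost nothing and replaces a contrast that cannot answer the question.

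**What to change.** Replace the comparison in Procedures, and add to the SAP, wording to this effect: month-12 IgG, IgA, IgM and IgE will be compared between OM-85 and placebo by ANCOVA with the baseline value as covariate, on the log scale where the distribution is skewed. This analysis is exploratory. Changes from baseline within each arm will be summarised descriptively, without P values.

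The cost is two or three sentences. Both samples are already planned in both arms, so no visit, blood draw or patient is added. It should be written in before the data are unblinded.

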Appendix 1. Study Forms

Table 1. Demographic charecteristics

PATIENT FOLLOW-UP FORM		
Date		
Patient Number		
Treatment group (Randomisation code)		
Name Surname		
Birth date		
Gender		
Smoking at home		
Family history of asthma		
Family history of atopy		
DPT		
lgG		
IgA		
lgE		
IgM		
FIRST VISIT		
RTIs in previous 12 months		
RTIs in previous 6 months		
Number of hospitalisation in previous 12 months		
Total days of hospitalisation in previous 12 months		
Total days of absenteisim from school		
Total days of absenteisim from work for mother		
Total days of absenteisim from work for father		
Antibiotic use in previous 12 months		
Number of box		
Total number of days		
Symptome score		

QoLQ (Score)	
Adenoid size	
Radiological (AC/SP ratio)	
Nasopharingoscope (perceived percent obstruction of the choana)	

Table 2. Symptomes score (will be completed for each month)

Symptomes	none (0 point)	rarely (1 point)	frequently (2 points),	constantly (3 points)
Snoring				
mouth breathing awake				
mouth breathing asleep				
nasal congestion				
hyponasal voice				
chronic nasal discharge				
daytime drowsiness, or hyperactivitiy				
restless sleep				
sleep apnea <15 sec				
night cough				
poor oral intake/weight loss				

Scores from eleven symptoms were added together to provide a total symptom score of 33.

Table 3. Infection form (will be completed for each infection)

Type of RTI	
Duration of RTI	
Antibiotic consumption (days)	
Days of absenteism from school	
Days of absenteism from work for family members	

Table 4. Tonsil and Adenoid Health Status Survey (It will be completed by the parents in every
3 months)

TONSIL AND ADENOID SURVEY

We are conducting a study on children with tonsil or adenoid problems, and we are interested in the type of health problems that your child is having related to his (her) tonsils and adenoids. There are no correct or incorrect answers, and your opinion is most important to us. The survey is completely voluntary and will take about 3 minutes to complete.

Please answer these questions remembering the past 6 months for your child. The questions relate to the problems many children have related to their tonsils and adenoids. If a certain question is not a problem for your child, please circle "0" (not a problem) for that question. Please do not skip questions or leave any questions unanswered.

.....

Over the past 6 months, how much of a problem were the following conditions for your child?

Please circle the most correct response

		Nict a problem	very mild problem		fairly bad problem	severe problem	
1.	Snoring loudly during sleep	0	1	2	3	4	1
2.	Strep throat infections	0	1	2	3	4	2
3.	Many trips to a doctor's office	0	1	2	3	4	3
4.	Taking antibiotics for more than 3 weeks straight	0	1	2	3	4	4
5.	Taking antibiotics over and over for less than 2 weeks at a time	0	1	2	3	4	5
6.	Many calls to a doctor's office	D	1	2	3	4	8
7.	Irregular or stopped breathing, also known as apnea, during sleep	D	1	2	3	4	,
8.	Repeated short-term (or acute) infections of the tonsils that last less than 2 weeks	D	1	2	3	4	a
9.	Constant, or chronic, infection of the tonsils that last more than 2 weeks	D	1	2	3	4	9
0.	The cost of medical care and prescriptions	D	1	2	3	4	16
1.	Breathing through the mouth during the day	0	1	2	з	4	11
2.	Your child not growing or gaining weight as expected	0	1	2	з	4	12
13.	Noisy breathing during the day	D	1	2	3	4	12
4.	Problems with poor appetite or poor eating habits	0	1	2	3	4	14
5.	Behavior problems at home or at school, or poor school grades or reports	0	1	2	3	4	11

Table 5. Follow-up form

Visit (3-6-9-12 months)	Date:					
Number of RTIs in previous 3 months:						
• Туре	AOM	AS	AT	AN	AC	Р

Number					
Duration (days)					
Antibiotic use in previous 3 months					
• Туре					
Number (box)					
Duration (days)					
Hospitalisation:	(((($\overline{(0)}$	$\overline{(1111)}$	(((($\overline{(00)}$
Number					
Duration (days)					
Symptome score					
QoLQ (Score)					
Adenoid size					
Radiological (AC/SP ratio)					
 Nasopharingoscope (perceived percent obstruction of the choana) 					

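### The Tonsil and Adenoid survey recalls 6 months but is given every 3 months, so half of the month-3 window nominally precedes treatment; compare the arms at months 6 and 12, adjusted for baseline

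*Protocol*

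**What the plan says.** - **Recall period.** The form in Protocol Appendix 1, Table 4 instructs: "Please answer these questions remembering the past 6 months for your child". The stem above the items repeats the 6-month period.
- **Frequency.** Protocol, Procedures: "Every 3 months they will fill in the Tonsil and Adenoid Health Status Survey (Table 4"). Table 5 places follow-up at months 3, 6, 9 and 12 and has a line for the survey score. Table 1 records the score at the first visit too, so a baseline value exists.
- **Other items on the same visit form.** Table 5 asks for "Number of RTIs in previous 3 months", a window that matches the visit interval.
- **Endpoint.** Protocol, Endpoints, lists "Adenoid and tonsil survey (described in appendix 1 of the" original protocol) as a secondary endpoint, without a time point.
- **Analysis.** Protocol, Statistical Methods, and the SAP compare the arms on continuous variables by ANOVA or Mann-Whitney U, with no baseline covariate. The one rule about time is a Bonferroni comparison of "paired intervals (0-3, 0-6 months"). It names no variable and does not reach month 9 or 12.
- **Treatment timing.** Protocol, Procedures: "All patients will receive 2 cures of treatment at the beginning and 6 Months after inclusion in the study".

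**The concern.** A parent who follows the instruction at month 3 reports on three months before treatment and three months after its start. The earlier three were already reported on the baseline form. Several items count events (strep infections, doctor visits, antibiotic courses, repeated tonsil infections), so pre-treatment events are expected to enter the answer. Children qualify by having had at least 3 RTIs in the 6 months before inclusion, so the shared months carry a selected, high burden in both arms.

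Baseline and follow-up RTI windows also differ in length (Table 1 asks for the previous 6 and 12 months, Table 5 for the previous 3). But the month-3 RTI count does not reach back before treatment, whereas the survey does.

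The SAP neither assigns the survey a time point nor keeps it out of the 0-3 month comparison. At stake is a secondary result: a null month-3 survey comparison could be read as no early effect when the measure could show only part of one. No end-of-study survey comparison is named to set against it.

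**Working it through.** The documents give no effect, SD or sample size for the survey, so there is no survey figure to reproduce.

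**1. Recall windows.** A form completed at month m covers months m-6 to m.

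| Survey | Window (months) | Before treatment | Shared with baseline form |
|---|---|---|---|
| Baseline | -6 to 0 | 6/6 | n/a |
| Month 3 | -3 to 3 | 3/6 = 50% | 3 months |
| Month 6 | 0 to 6 | 0% | 0 |
| Month 9 | 3 to 9 | 0% | 0 |
| Month 12 | 6 to 12 | 0% | 0 |

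Months 6 and 12 share no time with each other. Month 9 shares 3 months with each of them.

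**2. Dilution in raw points.** Let D be the effect in each post-treatment quarter and w the weight parents give to the recent half of the window. The month-3 effect is wD and the month-6 effect is D, so the ratio is w: 0.50 with equal weights, 0.70 with w = 0.7.

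**3. Dilution of the standardised effect.** Assume quarterly scores Q-2, Q-1, Q1, Q2 with variance 1 and common correlation r. With equal weights:

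- B = (Q-2 + Q-1)/2, M3 = (Q-1 + Q1)/2, M6 = (Q1 + Q2)/2, each with variance (1+r)/2.
- Corr(B, M3) = (1+3r)/(2(1+r)); Corr(B, M6) = 2r/(1+r).
- Baseline-adjusted ratio, month 3 to month 6: 0.5 × sqrt[(1 - Corr(B,M6)²)/(1 - Corr(B,M3)²)] = sqrt[(1+3r)/(3+5r)]. This gives 0.577 at r = 0, 0.642 at 0.25, 0.674 at 0.5, 0.694 at 0.75, and 0.707 as r approaches 1.
- Change from baseline: Var(M3-B) = (1-r)/2 and Var(M6-B) = 1-r, so the ratio is 0.5 × sqrt(2) = 0.707 for any r below 1.

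With w = 0.7 the common variance is 0.58 + 0.42r, Cov(B, M3) = 0.21 + 0.79r and Cov(B, M6) = r. The adjusted ratio is 0.751 at r = 0, 0.843 at r = 0.5, and 0.876 as r approaches 1. For change from baseline it is 0.7 × sqrt(1.16/0.74) = 0.876.

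Adjustment recovers part of the loss because month 3 and baseline share recalled months, but not all of it.

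**4. Illustration in power.** This borrows the primary endpoint's planning values only to give a scale. The standardised effect is 2.0/2.55 = 0.784. A two-sided 0.05 t test with 27 per group has 80.7% power, which agrees with the plan's claim of at least 80% for RTIs. Halving the effect to 0.392 gives 29.3%. With 60% to 90% of the weight on the recent half, power is 39.6% to 72.1%.

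**5. Sensitivity to visit timing.** The visit table after Planned Timelines puts visit 4 at 3 months after the last intake. If the last dose is near day 70, that is 70 + 91 = day 161, and (183 - 161)/183 = 22/183 = 12% of the recall window would precede treatment. Table 5 puts the visit at month 6, where the share is 0%.

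**The case against.** The strongest reply is that the harm is conditional and small. No passage says the month-3 survey score will be tested. Dilution is conservative: the pre-treatment half has the same expected content in both randomised arms. Other data speak to early effects, namely the monthly symptom score in Table 2, which overlaps several survey items, and the 3-month RTI and antibiotic counts in Table 5. All of this stands. It limits the point to one secondary endpoint but does not remove it, because the survey still has no time point and the named 0-3 month interval is the affected one.

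The ratios in steps 2 and 3 rest on assumptions, in particular an equal effect in both post-treatment quarters, although the first includes dosing and the second does not. That is fair: with unequal effects the month-3 to month-6 ratio could leave the stated range. The 50% share does not depend on it. Nor does the raw dilution relative to the true first-quarter effect, which stays at w.

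The month-6 window is wholly post-treatment only on Table 5 timing. On the visit-table reading about 12% precedes treatment. If the second course starts at that visit and the pattern repeats, visit 6 falls near day 322 and its window (from day 139) overlaps visit 4's by 161 - 139 = 22 days. The passages need reconciling, but 12% is far below 50%.

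Finally, baseline adjustment is a general efficiency gain and does not follow from the recall window; an unadjusted randomised comparison is valid. True, but the score is already collected, and adjustment multiplies the variance by 1 minus the squared correlation: 0.91, 0.75 and 0.51 for assumed correlations of 0.3, 0.5 and 0.7.

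**Conclusion.** The concern holds. On the nominal schedule, half of the month-3 recall window precedes treatment and repeats the second half of the baseline window. The plan does not keep the survey out of the 0-3 month comparison and names no survey comparison at month 12.

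The 50% share follows directly from the documents. The loss of effect does not: under the stated assumptions the month-3 effect is 0.50 to 0.70 of the month-6 effect in raw points, and about 0.58 to 0.88 once standardised with adjustment for, or change from, baseline. The error is toward zero, type I error is kept, and the primary endpoint and sample size are untouched. This should be corrected in the SAP, but it does not threaten the trial's main conclusion.

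**What to change.** Add to the SAP:

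- The between-arm survey comparison is made at months 6 and 12, in a linear model with treatment arm and the baseline survey score. Naming the model matters because Mann-Whitney U takes no covariate. State which time point is the main one, or split the 0.05 between them (0.025 each).
- The survey is left out of the 0-3 month comparison. Month 3 is reported descriptively, with a note that half of its recall window precedes treatment. Month 9 can also be descriptive, because its window overlaps those of months 6 and 12 by 3 months each; it is not affected by the pre-treatment period.
- The visit table and Table 5 are reconciled on when visits 4 and 6 take place, so that the recall windows are defined.

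The nominal windows for months 6 and 12 (0 to 6 and 6 to 12) do not overlap each other or baseline, and each corresponds to one treatment course. The questionnaire, visit schedule and sample size stay as they are. The cost is a few sentences and the loss of a diluted month-3 test.

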	Sample Size:					
	In one study OM-85 group showed 3 less RTIs compared with					
	placebo over 12 months period. A sample size of 54 randomized					
	patients (27 per group) will provide at least 80% power to detect a					
	mean difference of at least 2.0 RTIs between the two groups					
	assuming a SD of 2.55 and assuming a drop-rate of 20% after 6					
	months, total of 68 patients (34 per group) will recruit to the study. ¹					
	Reference:					
	1. María Dolores Gutiérrez-Tarango and Arturo Berber. Safety and Efficacy of Two Courses of OM-85 BV in the Prevention of Respiratory Tract Infections in Children During 12 Months.					
	CHEST 2001; 119:1742–1748					
Planned Timelines	Planned date first patient consented/enrolled/observed: 01					
	September 2017					
	Planned date last patient consented/ enrolled/ observed: 01 March					
	2018					
	Planned date last patient last observation/ treatment: 01 March 2019					
	Planned date CSR (Clinical study report) available: June 2019					

1. Visit	2. Visit	3. Visit	4. Visit	5. Visit	6. Visit
Randomitaz ion of the patients	After randomization treatment plan (OM-85 capsules or placebo given in the first 10 days of each month for 3 months)	Control at the end of 3rd month of treatment (20 days after the last medicine/drug or placebo)	Control after 3 months of last drug or placebo intake and Given the product by the previous randomization again for 3 months	At the end of the second 3-month treatment (20 days after the last drug)	Control after 3 months of the last drug or placebo intake (20 days after the last medicine/drug or placebo)

• Patients will be assessed for type of respiratory infection and additional treatment by researchers (pediatric allergy specialists and/or ENT specialists) in the Pediatric Allergy and Immunology outpatient clinic when symptoms of respiratory tract infection is present.

- Parents will be asked to fill in the relevant form [Symptom Score Form] during this acute respiratory tract infection.
- Every 3 months, parents will be filled.QoLQ "Tonsil and Adenoid Health Status Survey".

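### The follow-up form's fixed 3-month look-back covers the year exactly once only if visits fall exactly at months 3, 6, 9 and 12, and the protocol's visit table conflicts with that spacing

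*Protocol*

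**What the plan says.** **Endpoint.** Protocol, Endpoints: "Primary Endpoint: Cumulative number of RTIs over the 12" months. Protocol, Procedures: "Every patients will be followed-up for 12 months".

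**Form.** Table 5 (Protocol, Appendix 1) is the only printed follow-up form with a field for the number of RTIs. It asks for "Number of RTIs in previous 3 months" and "Antibiotic use in previous 3 months". Its header reads "Visit (3-6-9-12 months", and Procedures agrees: "Every 3 months patients will be asked to come to the clinic and all their records will be collected".

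**Visit table** (Protocol, after Planned Timelines). Visit 3 is "Control at the end of 3rd month of treatment (20 days after the last medicine/drug or placebo". Visit 4 is "Control after 3 months of last drug or placebo intake", measured from that same intake. Visits 5 and 6 repeat the pattern after the second course, but the Visit 6 cell gives both 3 months and 20 days after the last intake.

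**Other records.** Children are asked to attend when they have RTI symptoms, and Table 3 is completed for each infection. Table 3 has type, duration, antibiotic days and absenteeism, but no onset date. Procedures says that RTI duration and antibiotic use are also recorded monthly on Table 2, but Table 2 as printed contains only symptom rows.

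Neither the Protocol nor the SAP says which form supplies the primary count, or how it is derived.

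**The concern.** A look-back of fixed length is safe only when visits are spaced by exactly that length. With shorter spacing, an RTI in the overlap can be entered on two forms. With longer spacing, or a last visit before month 12, an RTI can be entered on none. The visit table puts Visits 3 and 4 about 70 days apart, so a 3-month question at Visit 4 repeats about 20 days that Visit 3 has already covered.

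At stake is the 12-month RTI count, which is the primary endpoint. The Table 5 entries for RTI duration and antibiotic use have the same weakness. Without onset dates on Table 3, a duplicate or an episode outside the 12 months cannot be identified from the forms as printed.

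**Working it through.** **The plan's own figure.** Inputs from SAP, Sample Size: difference 2.0, SD 2.55, 80% power, two-sided 5%. Normal approximation: 2 × (1.96 + 0.842)² × 2.55² / 2.0² = 25.5, so 26 per group. By the noncentral t distribution, power is 79.2% at 26 and 80.7% at 27, so 27 per group is reproduced. For 20% dropout, 27 / 0.8 = 33.75, so 34 per group and 68 in total. The sample size is sound on its own assumptions.

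**Visit days.** I use 30-day months, a 360-day year and a 90-day look-back. Dosing in the first 10 days of three consecutive months puts the last intake of course 1 at about day 70.

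- Visit 3: 70 + 20 = day 90.
- Visit 4, literal: 70 + 90 = day 160.
- Course 2 given at Visit 4: last intake 160 + 70 = 230; Visit 5 = 250; Visit 6 = 230 + 90 = 320.
- Course 2 at 6 months after inclusion (day 180): last intake 250; Visit 5 = 270; Visit 6 = 340.

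The 20-day wording for Visit 6 would put it on the same day as Visit 5, so it is not carried forward.

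**Coverage.** Each visit covers the 90 days before it.

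| Reading | Visit days | Days counted twice | Days uncovered |
|---|---|---|---|
| Table 5 header and Procedures | 90, 180, 270, 360 | 0 | 0 |
| Visit table, course 2 from Visit 4 | 90, 160, 250, 320 | 40 (70–90, 230–250) | 40 (320–360) |
| Visit table, course 2 at 6 months | 90, 160, 270, 340 | 40 (70–90, 250–270) | 40 (160–180, 340–360) |
| Visit 4 at 6 months, Visit 6 at 3 months after intake | 90, 180, 270, 340 | 20 (250–270) | 20 (340–360) |

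With a 365-day year and 91-day windows, the second and third rows become 41 and 43, and 40 and 42.

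**In RTIs.** Entry requires at least 3 episodes in 6 months, so I assume 6 per year, with a range of 4 to 8. For 40 days: 6 × 40/360 = 0.67 doubled and 0.67 missed per child (4 × 40/360 = 0.44; 8 × 40/360 = 0.89). For 20 days: 0.33 each.

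**Early or late attendance.** Suppose visits are at months 3, 6, 9 and 12, except that the month-6 visit falls on day 166. Its window is 76–166, so days 76–90 are doubled and 166–180 are missed. If it falls on day 194, days 90–104 are missed and 180–194 doubled. Each 14-day stretch is worth 6 × 14/360 = 0.23 RTIs.

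**Effect on the analysis if Table 5 entries are summed.** In the 40-day cases the windows still total 280 × 1 + 40 × 2 = 360 days, so at a constant rate the expected count is unchanged. The variance is not. With Poisson episodes the added variance is (rate/360) × (280 × 1² + 40 × 2² − 360) = (6/360) × 80 = 1.33. The SD becomes √(2.55² + 1.33) = 2.80 (2.72 to 2.88 for 4 to 8 per year). Normal-approximation power at 27 per group falls from 82% to about 75% (77% to 72%).

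**Which days.** The doubled days directly follow each last intake (70, 230 or 250). Every uncovered day lies 90 days or more after one. If any effect wanes, or RTI rates vary by season, the sum weights periods unequally.

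**With a since-last-visit question.** Double counting and mid-study gaps go to zero under every row. The tail stays uncovered: 40 days if Visit 6 is at day 320, 20 days if at day 340.

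**The case against.** The strongest reply is that the form and Procedures both specify 3-monthly visits, on which nothing is doubled or missed. The visit table may be loose wording, and its Visit 6 cell contradicts itself. This stands: a reader might infer that the protocol fixes an 11–12% miscount, but 40 days is the top of a range that starts at 0. The conflict remains, though, and no visit window is stated, so even the 3-monthly schedule depends on punctual attendance.

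Second, a reader might infer that the primary endpoint is the sum of the Table 5 entries. The documents do not say so. Each RTI should bring a clinic attendance and its own form, and an investigator working from collected forms need not enter an episode twice. That is a fair reading, but without an onset date Table 3 cannot show that it was done.

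Third, it is tempting to set 0.67 doubled RTIs against the target difference of 2.0, or to infer bias between arms. Neither is supported. Doubled and missed counts cancel in expectation at a constant rate, the schedule is the same in both blinded arms, and nothing indicates that attendance timing differs by arm.

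Fourth, not all missed days come from the recall window. If course 2 starts at Visit 4, all 40 fall after Visit 6; if at 6 months, 20 of the 40 do. This stands, and it is why visit timing must be part of the fix.

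**Conclusion.** The point holds as a weakness in how the primary count is captured. A fixed 3-month look-back is reliable only with exact 3-month visits, the visit table conflicts with that spacing, and no recorded onset date allows correction. The size is 0 to about 40 days doubled and the same uncovered, depending on the reading. That is 0 to about 0.7 RTIs per child each way at an assumed 6 per year (at most 0.44 to 0.89 for 4 to 8). If Table 5 entries are summed, the consequence is mainly noise, with power at worst around 72% to 77%, plus altered weighting of periods. The power figures are illustrative: they rest on assumed rates, Poisson episodes and literal visit-table timing. The documents show no bias between arms.

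**What to change.** 1. In Table 5, change both look-back headings (RTIs and antibiotic use) to *since the last visit (date __) up to today*.
2. Add an onset date to the Table 3 infection form.
3. State in the Protocol and SAP that the primary count is the number of distinct RTIs with onset from randomisation to month 12, each counted once, and name the form that supplies it.
4. Reconcile the visit table, including the two timings in the Visit 6 cell, with the month 3, 6, 9 and 12 schedule so that the last form reaches month 12. Rewording the window alone does not recover days after an early Visit 6. The passages on the start of the second course also need reconciling. That choice is the sponsor's, and items 1 to 3 work under either.

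The cost is minor form edits, one added date field and a sentence in each document. Procedures already plans immunoglobulin measurement at 12 months, so a contact at month 12 is already foreseen.
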